### **8.5 72 Hour Visit / Discharge (+/-12 hrs.) (whatever comes first)**

- NIHSS
- Standard of Care anti-thrombotics started by end of day 2

### **8.6 Hospital discharge**

- Concomitant antithrombotic medications during hospital course
- Anticoagulant deep vein thrombosis (DVT) prevention therapy during hospitalization
- Vascular medications at discharge (anticoagulants, antiplatelets, antihypertensives, statins, antidiabetics, cholesterol reducers)
- Stroke mechanism – TOAST criteria
  - 1) large-artery atherosclerosis
  - 2) cardioembolism
  - 3) small-vessel occlusion
  - 4) stroke of other determined etiology
  - 5) stroke of undetermined etiology
- Discharge destination (home, other acute hospital, acute rehab, skilled nursing facility, hospice, expired)
- Ambulatory status at discharge (independent, with assistance, unable)
- mRS at discharge
- AEs, SAEs, and UPs

### **8.7 Day 30 (±5) Visit**

- mRS
  - NIHSS
-

- Discharge Summary
- Concomitant medicines
- AEs, SAEs, and UPs

### 8.8 Day 90 ( $\pm 7$ ) Visit

- mRS
- NIHSS
- Concomitant meds
- Laboratory studies
  - Pharmacokinetic profile of TS23 and evaluation of anti-drug antibodies to TS23 at 90 ( $\pm 7$ ) days. Specimens are processed and frozen at site for every 6-month batch shipping to core lab.
  - (CBC, CMP, and Lipid profile if collected as standard of care at 90 ( $\pm 7$ ) days).
- AEs, SAEs, and UPs

## 9 SAFETY ASSESSMENTS

### 9.1 Primary safety endpoint

ANY ICH visualized on the 30 ( $\pm 4$ ) h CT scan is the primary study endpoint for SISTER. This will be determined on the 30 ( $\pm 4$ ) h CT scan uploaded in the central imaging databank by local study personnel, by a trained neuroradiologist who is blinded to the participant's study group assignment.

### 9.2 Secondary safety endpoints

1. Incidence of symptomatic ICH within 30 ( $\pm 4$ ) h of study drug administration (SITS-MOST definition). ([Wahlgren, Ahmed et al. 2007](#)) The presence of type-2 parenchymal hematoma will be determined by a central, blinded, neuroradiologist and a worsening in NIHSS will be determined by the NIHSS reported on the study CRF by the local, certified, blinded assessors.
2. Incidence of non-ICH major or clinically relevant non-major bleeding within 30 days of study drug administration.

Non-ICH major bleeding is defined as clinically overt bleeding, that is not ICH, with one or more of the following:

- causing a fall in hemoglobin of 2 g/dL or more,
  - or leading to a transfusion of 2 or more units of packed red blood cells or whole blood,
-

- symptomatic and occurring in a critical site: intracranial, intraspinal, intraocular, pericardial, intra- articular, intramuscular with compartment syndrome, retroperitoneal,
- contributing to death.

Clinically relevant non-major (CRNM) bleeding is defined as overt bleeding not meeting the criteria for major bleeding that requires medical attention or is associated with discomfort for the subject such as pain, or impairment of activities of daily life.

All other overt bleeding episodes not meeting the criteria for major or CRNM bleeding will be classified as nuisance bleeding.

Symptomatic ICH, non-ICH major bleeding, and CRNM will be adjudicated by the study independent medical monitor (IMM)

3. Non-bleeding, SAEs within 90 ( $\pm 7$ ) days will be determined by direct interview during all study visits.
4. Incidence of stroke-related and all-cause deaths within 90 ( $\pm 7$ ) days will be determined by direct interview.
5. Plasma fibrinogen levels at 3 (+/-1) h after completion of TS23 therapy will be determined by laboratory testing of study-specific blood draw.

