TS23 inhibited a2AP activity in all participants, in a dose-related fashion, with maximum effects in the initial blood samples after IV dosing (Figure 6A). The duration of inhibition of a2AP was also dose related. a2AP activity was  $\sim$ >50% inhibited for hours to 4 days at dose 2.5 to 7.5 mg/kg. TS23 immediately activated fibrinolysis after dosing and increased D-dimer levels relative to baseline levels; D-dimer levels were higher in cohorts receiving higher doses of TS23 (Figure 6B). (D-dimer is a specific biomarker that indicates endogenous thrombus dissolution, even in normal, asymptomatic individuals). In addition, clots formed *ex vivo* from subject plasma obtained 24h after TS23 administration rapidly dissolved in a dose-dependent fashion, while control clots from normal blood donors did not dissolve within 120 min, the maximum time of monitoring. Thus, TS23 safely engaged and inactivated a2AP, in a dose-related fashion, triggering endogenous fibrinolysis *in vivo* and clot dissolution *ex vivo*.

Figure 6. Dose-related Effects of TS23 on a2AP Activity and D-dimer Levels in Humans

A) a2AP inhibition was measured in a clinically validated plasma assay at baseline and at the indicated time points following a dose of TS23. B) D-dimer levels were measured in participants at baseline and at the indicated time points following a dose of TS23. Means  $\pm$  SE are shown for each dose cohort.

Please see the current version of the [Investigator's Brochure](#) for further information on the Phase 1 Clinical study results for TS23 (a2AP-I).

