#### **Safety:**

1. Incidence of symptomatic ICH within 30 ( $\pm 4$ ) h of study drug administration (SITS-MOST definition) ([Wahlgren, Ahmed et al. 2007](#))
2. Incidence of non-ICH major or clinically relevant non-major bleeding within 30 days of study drug administration.
3. Non-bleeding, SAEs within 90 ( $\pm 7$ ) days
4. Incidence of stroke-related and all-cause deaths within 90 ( $\pm 7$ ) days
5. Plasma fibrinogen levels at 3 ( $\pm 1$ ) h after completion of TS23 therapy

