## 4.3 Justification for Dose

The Phase II SISTER Trial seeks to identify the optimal dose of TS23 that is safest and most effective at reducing neurological deficits in ischemic stroke vs. control. The doses chosen in this study (3, 5, 7 and 10 mg/kg up to a max of 1000 mg) are within the range of TS23 dosing that was shown to be safe in phase-I human studies (2.5-10 mg/kg; as noted above). Since thrombus dissolution increases significantly when a2AP levels are less than ~50%, we selected a dose range of TS23 (3-10 mg/kg) that inhibits a2AP activity by ~50% to >95%.

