### **9.3.7 Adverse Events of Special Interest**

Adverse Events of Special Interest should always be reported to the Sponsor as soon as possible following the procedures outlined in Section 9.3.5 for Adverse Event reporting, with the Investigator's assessment of seriousness, causality, and a detailed narrative.

These include:

- Combined elevations of aminotransferases and bilirubin, either serious or nonserious and whether or not causally related, meeting the criteria of a potential Hy's Law case (total bilirubin level  $\geq 2 \times$  upper limit of normal (ULN) with simultaneously ALT or AST  $\geq 3 \times$  ULN).
- Symptomatic ICH as defined above.

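### A non-fatal intracranial hemorrhage after about 34 hours is counted in no hemorrhage or SAE endpoint, although a2AP inhibition can last up to 4 days

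*Protocol*

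**What the plan says.** ICH enters the protocol's endpoints in two places. The primary safety endpoint (Sections 1.1, 3.2 and 9.1) is any ICH on a CT taken 30 (±4) h after study drug. The secondary one, in Section 9.2, is "Incidence of symptomatic ICH within 30 ( $\pm 4$ ) h of study drug administration (SITS-MOST definition". The synopsis gives ±6 h for that item, while the definition bracketed inside the same item gives ±4 h.

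The other safety endpoints that could hold a clinical event read as follows.

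- Bleeding to day 30 (Section 9.2): "Non-ICH major bleeding is defined as clinically overt bleeding, that is not ICH, with one or more of the following". The list that follows nevertheless names intracranial among the critical sites.
- SAEs (Section 3.2): "Non-bleeding, SAEs within 90" (±7) days.
- Deaths, stroke-related and all-cause, to 90 (±7) days.

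Section 9.3.7 adds an adverse event of special interest: "Symptomatic ICH as defined above".

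On how long the drug acts, Section 2.4 reports from Phase 1 that a2AP activity was ">50% inhibited for hours to 4 days at dose 2.5 to 7.5 mg/kg", and adds: "The duration of inhibition of a2AP was also dose related". Section 4.3 ties that level to effect: "thrombus dissolution increases significantly when a2AP levels are less than ~50" per cent. Section 8.5 lists, under the 72 h visit, "Standard of Care anti-thrombotics started by end of day 2".

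**The concern.** The primary objective is to identify a dose that is safe, and Section 3.3 names symptomatic ICH among the most feared complications of this type of drug. Yet ICH is counted only up to about a day and a half, while the protocol's own Phase 1 summary has the target more than half inhibited for as long as 4 days. On the efficacy side the protocol allows for a lasting effect: Section 3.3 adds the 72 h NIHSS for that reason. ICH has no counterpart.

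The later days also differ from the first. Section 6.1.1 withholds antithrombotics for at least 24 h and says that bleeding risk may be higher when they are given together with TS23. Section 8.5 has them started by the end of day 2. Much of that overlap falls after the last ICH assessment.

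At stake is what the trial can say about a safe dose. A dose could be reported with no excess of symptomatic ICH while events on days 2 to 4 stand outside every hemorrhage and SAE endpoint. If late ICH risk follows the duration of inhibition, a comparison between doses could be affected too.

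**Working it through.** The protocol states no figure on this point, so there is none to reproduce. The check is to follow one case through the endpoints and then set the time limits against the stated duration of inhibition.

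**Step 1. A test case.** Take a non-fatal symptomatic ICH 60 h after study drug (a time chosen for illustration).

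| Endpoint or category | Where | Counted? |
|---|---|---|
| Any ICH on the 30 (±4) h CT | 1.1, 3.2, 9.1 | No, the scan precedes the event |
| Symptomatic ICH within 30 (±4) h | 3.2, 9.2 | No; the ±6 h in 1.1 does not change this |
| Major or clinically relevant non-major bleeding to day 30 | 9.2 | No by the stem; the critical-site list contradicts the stem |
| SAEs to day 90 | 3.2, 9.2 | No, bleeding events are excluded |
| Deaths to day 90 | 3.2, 9.2 | No, the event is not fatal |
| Special-interest event | 9.3.7 | No, it takes over the 30 h definition |

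The Schedule of Activities has no brain imaging after the 30 h visit.

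**Step 2. Where counting stops.** Upper limit = 30 + 4 = 34 h. With the synopsis figure it is 30 + 6 = 36 h. The CT itself may be taken as early as 30 − 4 = 26 h.

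**Step 3. Against the duration of inhibition.** The upper end in Section 2.4 is 4 × 24 = 96 h.

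- After a 34 h limit: 96 − 34 = 62 h remain.
- After a 36 h limit: 96 − 36 = 60 h remain.
- After a CT at 26 h: 96 − 26 = 70 h remain for a bleed that only imaging would show.
- At the lower end (hours; 24 h taken as an assumption) nothing remains, because 24 < 26.

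These are hours above a pharmacodynamic threshold. They do not measure bleeding risk. Section 2.4 puts the maximum effect in the first samples after dosing, so the 30 h window does cover the peak. The range of hours to 4 days applies to 2.5 to 7.5 mg/kg as a whole. No duration is given for any single trial dose, and none at all for 10 mg/kg.

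**Step 4. The dose decision.** In Section 10.2.2 the safety term of the utility is ICH on the follow-up CT. Late ICH therefore does not enter the utility. That is a reasonable choice for a quantity updated every 50 subjects, but it means that late ICH would have to be seen through another endpoint, and Step 1 finds none.

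**The case against.** The strongest reply is that late ICH is neither lost nor unseen. AEs and SAEs are collected to the 90-day visit (Section 9.3.4). The independent medical monitor (IMM) reviews every SAE, and the DSMB's closed reports give summaries by partially blinded treatment group, with full unblinding at its discretion (Section 9.5). All AEs count as unexpected for regulatory reporting (Section 6.1.1), and the study can be stopped for unacceptable risk (Section 11.1.2). A disabling bleed would also show, indirectly, in the 72 h NIHSS, depending on its timing, and in the 90-day mRS. Tables of bleeding SAEs by arm may be in the SAP, which is not at hand.

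This stands as far as oversight goes. It does not answer the point about endpoints. NIHSS and mRS do not identify a bleed. Recording an SAE is also not the same as counting it in a prespecified, adjudicated endpoint by dose, and here the endpoint wording itself shuts the event out.

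A second reply is that the intracranial item in Section 9.2, or the clinically relevant non-major category, would admit a late ICH. The first reading conflicts with the stem of the same definition. The second would file a symptomatic brain hemorrhage as non-major bleeding. Either way the section needs correcting.

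A reader might go further and infer that the window favours the higher doses. The documents do not support that. It requires late ICH risk to follow the duration of inhibition, and the protocol has no late-ICH data. What it cites points, if anything, the other way: no CNS hemorrhage in 14 people with a2AP deficiency (Section 2.2), and less ICH with a surrogate antibody in mice (Section 2.5.1). Antithrombotic use applies to every arm, placebo included, so it gives no dose direction by itself.

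**Conclusion.** The gap is real and follows from the wording alone. A non-fatal ICH after about 34 h (36 h by the synopsis) is counted in no hemorrhage or SAE endpoint, while a2AP may still be more than half inhibited. At the upper end of the Phase 1 range, 60 to 62 h of that period lie beyond the limit for symptomatic ICH. This rests on Phase 1 durations carrying over to stroke patients, on 4 days being the upper end for 2.5 to 7.5 mg/kg, and on reading the 30-day bleeding definition by its stem.

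Three stronger inferences are not supported. A bias toward higher doses is possible but unproven. Inhibition lasting beyond 4 days at 10 mg/kg is an extrapolation from the dose relation. The number of missed events cannot be derived, because the protocol gives no late-ICH rate, and a share of hours is not a share of risk.

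This should be fixed, because it limits what the trial can conclude about a safe dose. It does not undermine the design, the utility or the 30 h endpoints.

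**What to change.** Keep the 30 h endpoints and the utility unchanged, and amend the protocol as follows.

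1. Add a secondary safety endpoint: symptomatic ICH at any time from the start of study drug, through day 30 and through day 90, by arm. Sources are SAE reports and clinically obtained scans. The IMM, who already adjudicates symptomatic ICH under Section 9.2, adjudicates these too.
2. Replace the non-bleeding SAE endpoint with all SAEs to day 90, showing bleeding and non-bleeding events separately.
3. Remove the 30 h limit from the symptomatic ICH event of special interest in Section 9.3.7.
4. Reconcile, in Section 9.2, the exclusion of ICH with the intracranial critical site.
5. Reconcile ±6 h with ±4 h in the synopsis item on symptomatic ICH.

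The cost is protocol wording, adjudication of any late events and added safety tables by arm. Data collection already runs to day 90, so no new visit or scan is needed. The one drawback is that late events rest on imaging triggered by clinical need. They will be less uniform than the 30 h CT, and the report should say so.

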### **9.3 Adverse Events and Serious Adverse Events**

#### **9.3.1 Definition of Adverse Events (AEs)**

An AE is any untoward medical occurrence in a subject administered a pharmaceutical product that does not necessarily have to have a causal relationship with this treatment. An AE can therefore be any unfavorable and unintended sign (including an abnormal laboratory finding, for example), symptom, or disease temporally associated with the use of a medicinal product, whether or not considered related to the medicinal product (ICH E2A Guideline. Clinical Safety Data Management: Definitions and Standards for Expedited Reporting, Oct 1994).

It is the responsibility of Investigators, based on their knowledge and experience, to determine those circumstances or abnormal laboratory findings which should be considered AEs.

#### **9.3.2 Definition of Serious Adverse Events (SAEs)**

An SAE is any untoward medical occurrence that at any dose:

- Results in death,
  - Is life-threatening,
  - Requires inpatient hospitalization or prolongation of existing hospitalization,
-

- Results in persistent or significant disability/incapacity,
- Is a congenital anomaly/birth defect, or
- Is an important medical event.

Note: The term “life-threatening” in the definition of “serious” refers to an event in which the subject was at risk of death at the time of the event; it does not refer to an event which hypothetically might have caused death if it were more severe (ICH E2A Guideline. Clinical Safety Data Management: Definitions and Standards for Expedited Reporting, Oct 1994). Medical and scientific judgment should be exercised in deciding whether expedited reporting is appropriate in other situations, such as important medical events that may not be immediately life-threatening or result in death or hospitalization but may jeopardize the subject or may require intervention to prevent one of the other outcomes listed in the definition above. Examples include allergic bronchospasm, convulsions, and blood dyscrasias or development of drug dependency or drug abuse.

Note:

- Procedures are not AEs or SAEs, but the reason for the procedure may be an AE or SAE.
- Pre-planned (prior to signing the Informed Consent Form) procedures or treatments requiring hospitalizations for pre-existing conditions that do not worsen in severity are not SAEs.

### 9.3.3 *Classification of an Adverse Event*

#### 9.3.3.1 *Severity of Event*

The severity of AEs and SAEs will be reported using the grading system outlined in the NCI Common Terminology Criteria for Adverse Events Version 5.0 (CTCAE). The CTCAE provides a grading (severity) scale for each AE term and AEs are listed alphabetically within categories based on anatomy or pathophysiology. The CTCAE (v5.0) displays Grades 1-5 with unique clinical descriptions of severity for each AE based on this general guidance:

| CTCAE Severity Grading Summary |                        |
|--------------------------------|------------------------|
| Grade 1:                       | Mild AE                |
| Grade 2:                       | Moderate AE            |
| Grade 3:                       | Severe or Disabling AE |
| Grade 4:                       | Life-Threatening AE    |
| Grade 5:                       | Death related to AE    |

The complete definitions of these grades are:

---

- Grade 1: Mild; asymptomatic or mild symptoms; clinical or diagnostic observations only; intervention not indicated.
- Grade 2: Moderate; minimal, local, or noninvasive intervention indicated; limiting age-appropriate instrumental activities of daily living (preparing meals, shopping for groceries or clothes, using the telephone, managing money, etc.).
- Grade 3: Severe or medically significant but not immediately life-threatening; hospitalization or prolongation of hospitalization indicated; disabling; limiting self-care activities of daily living (bathing, dressing and undressing, feeding self, using the toilet, taking medications, and not bedridden).
- Grade 4: Life-threatening consequences; urgent intervention indicated.
- Grade 5: Death related to AE.

#### 9.3.3.2 *Relationship to Study INTERVENTION*

The Investigator should assess causal relationship between an adverse event and the study drug on the basis of his/her clinical judgment and the following definitions. The causality assessment must be made based on the available information and can be updated as new information becomes available.

- Related:
  - The AE follows a reasonable temporal sequence from study drug administration and cannot be reasonably explained by the subject's clinical state or other factors (e.g., disease under study, concurrent diseases, and concomitant medications).

or

- The AE follows a reasonable temporal sequence from study drug administration and is a known reaction to the drug under study or its chemical group or is predicted by known pharmacology.
- Not Related:
  - The AE does not follow a reasonable sequence from study drug administration or can be reasonably explained by the subject's clinical state or other factors (e.g., disease under study, concurrent diseases, and concomitant medications).

#### 9.3.3.3 *Expectedness*

The IMM will be responsible for determining whether an SAE is expected or unexpected. An SAE will be considered unexpected if the nature, severity, or frequency of the event is not consistent with the risk information previously described for the study intervention.

#### 9.3.3.4 *Action Taken Regarding Study Drug(s)*

- Dose Not Changed: No change in study drug dosage was made.
-

- Drug Withdrawn: The study drug was permanently stopped.
- Dose Increased: The dosage of study drug was increased.
- Not Applicable: Subject died, study treatment had been completed prior to reaction/event, or reaction/event occurred prior to start of treatment.

#### 9.3.3.5 *Other Actions Taken for Event*

- None
  - No treatment was required.
- Medication required.
  - Prescription and/or over the counter (OTC) medication was required to treat the adverse event.
- Hospitalization or prolongation of hospitalization required.
  - Hospitalization was required or prolonged due to the AE, whether or not medication was required.
- Other.

#### 9.3.3.6 *Adverse Event Outcome*

- Recovered/Resolved
    - The subject fully recovered from the AE with no residual effect observed.
  - Recovering/Resolving
    - The AE improved but has not fully resolved.
  - Not Recovered/Not Resolved
    - The AE itself is still present and observable.
  - Recovered/Resolved with Sequelae
    - The residual effects of the AE are still present and observable.
    - Include sequelae/residual effects.
  - Fatal
    - Fatal should be used when death is a direct outcome of the AE.
-

- Unknown

### **9.3.4 Time Period and Frequency for Event Assessment and Follow-Up**

The occurrence of an AE or SAE may come to the attention of study personnel during study visits and interviews of a study participant presenting for medical care, or upon review by a study monitor.

All AEs including local and systemic reactions not meeting the criteria for SAEs will be captured on the appropriate CRF. Information to be collected includes event description, time of onset, clinician's assessment of severity, relationship to study product (assessed only by those with the training and authority to make a diagnosis), and time of resolution/stabilization of the event. All AEs occurring while on study must be documented appropriately regardless of relationship. All AEs will be followed to adequate resolution.

Any medical condition that is present at the time that the participant is screened will be considered as baseline and not reported as an AE. However, if the study participant's condition deteriorates at any time during the study, it will be recorded as an AE.

Changes in the severity of an AE will be documented to allow an assessment of the duration of the event at each level of severity to be performed. AEs characterized as intermittent require documentation of onset and duration of each episode.

The study coordinator will record all reportable events with start dates occurring any time after informed consent is obtained until the patient completes their 90-day visit. At each study visit, the investigator will inquire about the occurrence of AE/SAEs since the last visit. Events will be followed for outcome information until resolution or stabilization.

